## Baseline study assessments.

After the patient has been consented and enrolled in the study, they will then complete the baseline patient assessments using VA Research Electronic Data Capture (REDCap) on IPad. Paper surveys will be used as a backup. Assessments will include the following:

- (1) Demographics: age, gender, income (covariates), marital status;
- (2) Baseline frequency of gout flares requiring treatment and baseline patient satisfaction with ULT treatment;
- (3) Baseline gout-specific HRQOL assessment using the gout assessment questionnaire (GAQ);
- (4) Alcohol use and BMI (covariates; exploratory outcomes since alcohol and higher BMI are associated with higher risk of incident gout, gout flares and higher sUA level (1, 26-28));
- (5) Blood draw for baseline sUA;
- (6) ULT non-adherence on self-reported questionnaire by Voils et al.;(29) and
- (7) Self-reported ULT use from non-VA sites (non-VA ULT use; sensitivity analyses). Patients' usual care serum urate values will be captured at this visit.

Additional information will be obtained including contact information, best time to contact and email address. Veterans will be provided with \$25 remuneration (VISA gift card or VA Form 10-7078 - Participant payment voucher) for completing study assessments at the screening and baseline visit. If payment voucher is used, participant will bring this voucher to agent cashier to receive \$25 on the same day. VA CDW and inpatient/outpatient SAS files assessed through the VINCI database. Medical records databases will be used to assess comorbidity, demographics (marital status) and baseline health care utilization and ULT medication adherence for the last 6-9 months (see eligibility criteria). Patients without DVD players will be provided with a DVD player to watch the DVDs at home at 2- and 4-months.

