## Study procedures at follow-up visits and data collection tools

Follow-up assessments will be done at 1-, 2-, 3-, 4-, 6-, 9-, and 12-months after the baseline visit. The 2- and 4-month visits will be completed via mail, the 3-, 6-, 9-, 12-month visits will be completed in-person lasting 30-60 minutes, and the 1- and 12-month assessments will be completed via phone lasting 15-minutes.

The primary time-point for analyses will be at 6-months. Assessments are kept short considering responder burden and to ensure study retention. Veterans will be provided with \$25 remuneration (VISA gift card or VA Form 10-7078 - Participant payment voucher) for completing the screening visit and each study assessment; an additional \$25 VISA gift card will be provided as VISA gift card or VA Form 10-7078 (Participant payment voucher) to those who perform both blood draws at baseline and 12-month end-of-study visits. If payment voucher is used, participant will bring this voucher to agent cashier to receive \$25 on the same day. 1-month follow-up will be done via a telephone-administered survey at the patient's convenience in their home, given that most assessments are patient-reported. This approach economizes on patient time compared to traditional gout RCTs, where patients are seen in the clinic every 1-3 months with visits lasting 1-3 hours including waiting time (plus travel time). 3-, 6- and 9-month visits will be in-person; MEMSCap data will be downloaded and other outcomes captured. To remind the patient of the follow-up assessments, a post-card (and emails, when applicable) will be mailed 1-week prior and phone call made 2-days prior to the follow-up. To minimize patient responder burden, Veterans are only completing assessments related to primary and select secondary study outcomes (including 4-item gout flare questionnaire at 6- and 12-month follow-up).

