The 12-month visit (end-of-study) will be in-person, similar to the baseline visit. The visit will be coordinated with a scheduled VA clinic visit, as much as possible. MEMSCap data will be downloaded and Veterans will complete a questionnaire assessing gout flares since last visit (including those requiring treatment) and patient satisfaction with treatment, as in 3-, 6- and 9-month follow-up. In addition, Veterans will be requested to get a blood draw for end-of-study sUA (secondary outcome)(32) and also complete GAQ as a gout-specific HRQOL measure and self-reported medication adherence questionnaire (exploratory outcomes). GAQ and sUA will be done only at 12-month follow-up (expected to take additional 30-minutes). Veterans unable to come to the study clinic for the 12-month visit will be offered sUA blood draw at their nearest CBOC (routine laboratory test) and the research associate will administer 12-month assessments via the phone interview.

Statistical Analysis.

- SA1: Improving ULT adherence, directly measured by using MEMS (Medication Event Monitoring System) Caps at 3, 6, 9 months (assess intervention's effect) and 12 months (assess durability of effect),
- SA2: Improving Gout flare rate, patient satisfaction and target serum urate (sUA) <6 mg/dl achievement, as indirect measures of better ULT adherence and important gout outcomes. We will also explore the effect of storytelling on health-related quality of life (HRQOL), self-reported ULT adherence, alcohol ingestion, body mass index (BMI) and gout-related inpatient and emergency room utilization.

For both Aims 1 and 2, descriptive statistics for demographics (age, race, income, marital status, time since diagnosis of gout) and clinical parameters (ULT adherence, # gout flares, satisfaction, serum urate, GAQ) will be examined. Given the two arm study design (storytelling vs. usual care), statistical procedures appropriate for two-group comparisons will be utilized to conduct crude as well as adjusted comparisons based upon the distributional nature of the outcome.

For the primary outcome of ULT adherence, an unadjusted analysis will be conducted using the two-sample ttest to compare ULT adherence across study arms at 3, 6, 9, and 12 months. Adjusted estimates of ULT adherence by study arm controlling for age, gender, income, alcohol, site, and other covariates will be conducted using ordinary least squares regression.

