Similar analyses will be conducted for the secondary outcomes defined in aim 2. When examining sUA level, analyses will also be adjusted for use of other medications that effect serum urate (diuretics, lipid-lowering agents, aspirin and angiotensin receptor blocking drugs etc.), BMI and alcohol use. For frequency of gout flares, analyses will also be adjusted for use of anti-inflammatory prophylaxis during initial ULT treatment. If the normality assumption is violated, nonparametric methods will be used, instead of the parametric tests.

Careful attention will be paid to the distributional assumptions for Poisson regression and methods to adjust for over-dispersion will be employed. Finally, separate logistic regression models will be used to measure treatment differences in the odds of achieving target serum urate <6 mg/dl and odds of healthcare utilization. To analyze the longitudinal data (1-, 3-, 6-, 9- and 12-months), we will use mixed linear models for ULT adherence (continuous outcome) and generalized estimating equations for target serum urate < 6 mg/dl, to analyze temporal relationships between the delivery of the intervention and medication adherence. All analyses will be guided by intent-to-treat analysis principles.

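### The longitudinal GEE for serum urate <6 mg/dl lists months 1 to 12, but urate is scheduled only at baseline and month 12; the month-12 logistic model should name baseline urate

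*Combined protocol and SAP*

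**What the plan says.** Three parts of the combined protocol and SAP bear on this point.

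**The models (Statistical Analysis).** The longitudinal sentence opens "To analyze the longitudinal data (1-, 3-, 6-, 9- and 12-months" and assigns a mixed linear model to adherence. For urate it assigns "generalized estimating equations for target serum urate < 6 mg/dl, to analyze temporal relationships between the delivery of the intervention and medication adherence". Just before it, the section states that "separate logistic regression models will be used to measure treatment differences in the odds of achieving target serum urate <6 mg/dl".

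**The draws.** Table 1 (Outcomes) lists serum urate at months 0 and 12. Baseline study assessments includes "Blood draw for baseline sUA". The follow-up section ties a payment to completing "both blood draws at baseline and 12-month end-of-study visits", and its account of the 12-month visit says "GAQ and sUA will be done only at 12-month follow-up".

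**The covariates (Statistical Analysis).** The general list is "controlling for age, gender, income, alcohol, site, and other covariates". For urate it adds: "When examining sUA level, analyses will also be adjusted for use of other medications that effect serum urate", together with BMI and alcohol use. Baseline urate is not named in either place.

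The follow-up section sets 6 months as the primary time-point. The Table 1 footnote reads 12-month results, for MEMS and for the secondary outcomes, as showing whether effects seen at 6 months last.

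**The concern.** A longitudinal model needs repeated values. Of the five months listed, four (1, 3, 6 and 9) have no scheduled urate draw. An analyst following the sentence literally could not produce a urate time course. A report following the footnote could present a month-12 urate result as the persistence of a 6-month effect that was never measured.

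The second issue is efficiency. Baseline urate is planned for every patient and is a natural predictor of month-12 urate, yet the plan does not commit to using it. Leaving it under unspecified other covariates also leaves the choice open until after data are seen.

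**Working it through.** **1. Schedules side by side.** The months listed for the longitudinal models are {1, 3, 6, 9, 12}. Their overlap with each Table 1 schedule is:

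| Outcome | Table 1 months | Overlap with the listed months |
|---|---|---|
| Serum urate | 0, 12 | 12 |
| MEMS adherence | 3, 6, 9, 12 | 3, 6, 9, 12 |
| Flares | 0, 1, 3, 6, 9, 12 | 1, 3, 6, 9, 12 |
| SATMED-Q | 0, 6, 12 | 6, 12 |

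Urate is the only one of the four with no 6-month value and with a single value in the listed months.

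**2. What the GEE becomes.** With one record per patient there is no within-patient correlation to model. In a simulated data set of 120 per arm, the GEE gave a log odds ratio of 0.814 (SE 0.270) with both independence and exchangeable working correlation. Ordinary logistic regression gave the same estimate and SE.

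**3. What baseline urate adds.** The plan states no figure to reproduce, and it gives no control rate or correlation for urate. Inputs:

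- Total of 300 patients (Introduction). 1:1 allocation is assumed.
- 20% dropout, assumed from the Patient retention section: 300 × 0.8 / 2 = 120 per arm.
- 30% versus 50% at target at month 12 (assumed). The 20-point gap takes Table 1's meaningful difference as absolute, which the table does not state.
- Correlation between baseline and month-12 urate of 0.3, 0.5 or 0.7 (assumed).

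The unadjusted 95% half-width for the risk difference is 1.96 × √(0.3 × 0.7/120 + 0.5 × 0.5/120) = 1.96 × 0.0619 = 12.1 points.

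The adjusted estimator is logistic regression on arm and continuous baseline urate, standardised to a risk difference. Its half-width is 12.1 × √(variance ratio). The last column compares models that both contain an assumed index of other covariates explaining 0–20% of urate variance.

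| Correlation | Variance cut, against unadjusted | Half-width (points) | Variance cut, against a model with other covariates |
|---|---|---|---|
| 0.3 | 4–5% | 11.8–11.9 | about 0–5% |
| 0.5 | 13–15% | 11.2–11.3 | about 6–15% |
| 0.7 | 26–31% | 10.1–10.4 | about 25–31% |

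These are simulation results and are good to a few percentage points.

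**4. A smaller effect, as a cross-check.** With 30% versus 45% at target and 120 per arm (two-sided 5%, 2,000 runs), power of the logistic test without and with baseline urate was 0.68 and 0.67 at correlation 0, 0.69 and 0.71 at 0.3, 0.66 and 0.74 at 0.5, and 0.67 and 0.82 at 0.7. Naming the covariate costs essentially nothing if it proves uninformative.

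**The case against.** **A GEE on months 0 and 12 is a legitimate model.** This stands. With a common baseline mean and exchangeable correlation (600 runs per case, 120 per arm, 30% versus 50%), the variance of its log odds ratio was about 0.98, 0.89 and 0.79 of the unadjusted month-12 logistic model at correlations 0.3, 0.5 and 0.7. A reader might infer that no GEE for urate is possible, or that deleting urate from the sentence gives up nothing. The documents do not support that: two values per patient are scheduled. But month 0 is not in the listed months, and two points still give no post-baseline course and no 6-month effect.

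**The month list is shared drafting, not a urate schedule.** This is fair in part. Month 1 is not in Table 1's MEMS schedule either. The sentence still names urate, so it needs reconciling with Table 1.

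**Interim values may exist.** Study Population, Outcomes and Baseline study assessments mention usual-care or VA laboratory data. Such values could supply some interim results, so the point is limited to scheduled draws. The plan gives no visit window or selection rule for them after baseline, and their timing would follow clinical care.

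**The footnote's asterisk sits on the MEMS row, and the table shows urate at 0 and 12.** This is true and lowers the risk of misreading. The footnote's wording nevertheless takes in the secondary outcomes.

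**Baseline adjustment is optional and already permitted.** This stands. The randomised month-12 comparison is valid without it, and the open-ended covariate lists leave room for it. Nor should the gain against an unadjusted comparison be read as the gain over the planned analysis, which already adjusts for other covariates. The last column of the table is the closer guide.

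**Conclusion.** The mismatch is in the current text and is settled by the documents alone. Scheduled urate draws cannot deliver the longitudinal analysis over the listed months, and they cannot support a statement that a 6-month urate effect was sustained. Over those months the GEE duplicates the planned logistic regression.

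Naming baseline urate is an improvement rather than the repair of an error. Against a model with other covariates, its gain in variance runs from about nothing to 31%. The size depends mainly on a baseline-to-month-12 correlation that the documents do not give, and also on the assumed 30% and 50% at target, 120 per arm, and covariate index.

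A reader might infer that the urate result or the trial's main conclusion is at risk. It is not. Urate is a secondary outcome, its month-12 comparison can be estimated and is valid as planned, and the primary MEMS outcome is unaffected. The change should be made, but nothing essential fails without it.

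**What to change.** 1. Remove serum urate from the longitudinal sentence and keep the mixed linear model for MEMS adherence. The sentence's stated purpose is the timing of adherence, for which the Outcomes section already plans exploratory use of the MEMS data.
2. State that the month-12 logistic regression is the between-arm analysis of urate <6 mg/dl. Add baseline urate from the baseline draw, as a continuous covariate in mg/dl, alongside the covariates already planned. The variance reductions above refer to the standardised risk difference, so report that with its 95% confidence interval beside the odds ratio.
3. Limit the Table 1 footnote to outcomes with both 6- and 12-month data: MEMS adherence, flares and SATMED-Q.

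If usual-care or VA laboratory urate values are to be used as well, give the visit windows and selection rule and label that analysis supportive.

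The cost is wording only, with no new visit or blood draw. The sponsor gives up the option of a two-point GEE. Its use of baseline information is roughly what adjusting for baseline as <6 yes/no recovers (variance ratios 0.78–0.98 for the risk difference), and the continuous covariate recovers more.

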#### Data management, quality assurance and monitoring.

Data management and quality assurance are particularly important for this study. Data from paper surveys and telephone interviews from baseline and follow-up visits will be entered by a trained and IRB-approved research assistant into the study database. [name] (WOC appointment, BHM VA), who has extensive experience in the design and management of database systems for large studies, will coordinate data management. Since

personal identifiers will be collected, all database versions will be stored on VA server with password protected electronic files. The survey will be merged with baseline enrollment data collected at BVAMC to create master SAS datasets. We will program logic and range checks in SAS 9.3 (SAS Cary, NC) to ensure timely identification of data fields requiring querying and clarification. A frequent multiple-backup strategy is proposed due to our desire not to lose any study data.

# Human subjects protection.

All research will be conducted at the Birmingham VA and Birmingham VA Health Services Research & Development Center. We have stringent protection against breach of confidentiality using secured servers and locked office spaces for data entry at the Birmingham HSR&D. All electronic data will be housed on the Birmingham HSR&D secure server, located behind VA firewalls. At the start of the study, all project team members will be trained in practices that ensure participants' confidentiality and privacy. We will work with the local OI&T to create a secure folder, which will be used to receive and share data between study sites. Access will be restricted to only those with appropriate IRB approval and will be monitored by BVAMC OI&T. No data will be transferred off the secure server. All paper records will be stored in a locked cabinet until such time that they are archived off-site. The Birmingham VAMC has a contract with a secure offsite Records storage facility. Records will be transferred in sealed boxes with documentation of chain of custody for transfer to this facility.

All data will be collected ensuring patient privacy and upholding highest standards for information security. Data will only be accessed by the approved study personnel listed in this protocol, who have all the necessary trainings required by the VA to access data. All study personnel who leave the study will be removed from the study. All access to research data will be removed from any study personnel who leave the study. All incidents related to data security will be immediately reported to ISO, Privacy officer, ACOS-research and the Chair of IRB committee. [name] will use his encrypted VA laptop for electronic communication related to the study. Data will be destroyed as per the VA regulations. The VA currently requires that data to be kept indefinitely as per the VA regulations. We will not use any non-VA devices for this project.

